# 3 Study Cohorts and Endpoints

# 3.1 Study Cohort for Correlates Analyses

Finalization of the primary study cohort for correlates analysis will take place before unblinding case/non-case and randomization arm information for correlates analyses. The default is for the primary study cohort to be the same as the cohort used in the primary analysis of vaccine efficacy against the primary endpoint in the protocol, except that availability of a Day 1 and Day 57 blood sample for antibody testing is also required. It may also be required to have results from all tests for SARS-CoV-2 infection on Day 57 samples [serology and/or nucleic acid amplification test (NAAT)].

Typically the primary analysis cohort is baseline SARS-CoV-2 negative participants in the per-protocol cohort, with the per-protocol cohort defined as those who received all planned vaccinations without any specified protocol deviations, and who were SARS-CoV-2 RT-PCR negative at the terminal vaccination visit. We refer to this cohort representing the primary population for correlates analysis as the Per-Protocol Baseline Negative Cohort. We will wait to fully understand all of the antigen and serology testing data that are available in the data set to finalize the definition of the primary analysis cohort. If a vaccine has high vaccine efficacy, it is possible that rare vaccine breakthrough cases will be individuals who were infected before the second vaccine dose, or soon after the first dose, but had unusually long time periods between SARS-CoV-2 acquisition and symptomatic infection (COVID) diagnosis. This situation could complicate the interpretation of correlates analyses. Therefore, we may conduct some correlates analyses that use a stringent criterion to include vaccine breakthrough cases in the analyses, such as requiring antigen negative tests at both the dose two visit and Day 57 and all serologies negative through Day 57.

As the primary analysis of vaccine efficacy is conducted in baseline negative individuals, correlates of risk (CoR) and correlates of protection (CoP) analyses are only done in baseline negative individuals, and the analysis of data from baseline positive individuals is for purposes of immunogenicity characterization, given too-few anticipated vaccine breakthrough study endpoints for CoR/CoP assessment (although if there are many baseline positive vaccine breakthrough endpoint cases that baseline positive subgroup analyses may be considered). In baseline negative individuals, antibody marker data in placebo recipients is relevant for verifying the expectation that almost all Day 57 marker responses will be negative, given the lack of SARS-CoV-2 antigen exposure.

#### 3.1.1 [With Day 29 markers]

If Day 29 markers are included, analyses of Day 29 correlates are done in the same cohort as studied for the analyses of Day 57 markers, except the time origin in correlates analyses is set at the Day 29 visit and the set of participants included in the analysis is augmented with intercurrent cases. Intercurrent cases are defined as participants who were diagnosed with the COVID primary endpoint  $\geq$  7 days post Day 29 visit plus baseline negative cases with endpoint  $\geq$  6 days post Day 57 visit. These intercurrent cases are not included in the Day 57 marker correlates analyses for which cases are counted starting 7 days after the Day 57 visit. Thus, intercurrent cases are exactly the set of cases included in Day 29 correlates analyses but excluded from Day 57 correlates analyses. Analyses that include both Day 29 and 57 markers use the same cohort as for analyses of Day 57 markers only.

## 3.2 Study Endpoints

Endpoints for per-protocol correlates analyses of Day 57 markers are included if they occur at least 7 days after the Day 57 visit, to help ensure that the endpoint did not occur prior to Day 57 antibody measurement. Thus participants with a per-protocol endpoint diagnosed earlier are excluded from the Day 57 marker per-protocol correlates analyses.

Figure 1 defines five study endpoints that are assessed in COVID-19 vaccine efficacy trials, where all trials use COVID (symptomatic infection) as the primary endpoint. While the severe COVID endpoint is of paramount clinical importance, likely the number of events at the time of the first correlates analysis will be too small to assess correlates against this endpoint, such that correlates analyses will be done once more endpoints have accrued through longer-term follow-up.

In contrast, depending on the estimate of vaccine efficacy, there may be enough data to assess correlates against the endpoints non-severe COVID, SARS-CoV-2 infection (COV-INF), asymptomatic infection (ASYMP-COV-INF) at or shortly after the time of the first correlates analysis, and viral load at COVID diagnosis. Similar statistical methods can be used for each endpoint, with some distinctions that we discuss below in "General Statistical Issues in Correlates Assessment."

When a correlates analysis is done, all available follow-up for participants is included through to the time of the data base lock for the correlates analysis, for every CoR and CoP analysis that is conducted. This means that the time of right censoring for a given failure time endpoint will be the first event of loss to follow-up or the date of administrative censoring defined as the last date of available follow-up. For CoP analyses, which use both vaccine and placebo recipient data and leverage the randomization, follow-up is censored at the time of unblinding. In general all blinded follow-up is included and no post-unblinding follow-up is included.

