# 4 Objectives of Immune Correlates Analyses of a Phase 3 Trial Data Set

#### 4.1 Characterize Vaccine Immunogenicity

There are two objectives to characterize the binding and neutralizing antibody immunogenicity of the vaccine:

Stage 1 To characterize vaccine immunogenicity (bAb, nAb) at Day 1, 29, 57

Stage 2 To characterize vaccine immunogenicity/durability (bAb, nAb) over time (Day 1, 29, 57, 209, 394, 759)

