Table 3 summarizes one possible set of requirements for a Day 57 antibody marker to be accepted as a *validated surrogate* for a COVID-19 disease endpoint for use in approving COVID-19 vaccines for specific populations (e.g., SARS-CoV-2 seronegative adults) using Fleming and Power's definition. These potential requirements are conjectures provided for conceptualization purposes, and are not based on COVID-19 regulatory guidance documents.

Requirements (16. Required)	Endpoints and Evidence Bar
1. Strong evidence for CoR and CoP	COVID and VL endpoints: Highly
in vaccine recipients in animal	significant and predictive
and/or human challenge models	and Severe COVID : Point estimates
,	in the right direction
	and COV-INF, ASYMP-COV-INF: No
	countervailing evidence 
2. Strong evidence that the marker	
is a mechanistic CoP or tightly	Study endpoints used
correlated with a mechanistic CoP	in challenge models
(likely deriving from animal challenge	such as subgenomic
studies of vaccines or passively	SARS-CoV-2 RNA
transferred antibodies)	
3. Supportive evidence from natural history	Same endpoints as in Phase 3 trial
studies of CoRs of re-infection in	(COVID, severe COVID,
SARS-CoV-2 infected individuals	ASYMP-COV-INF, COV-INF, VL Dx)
4. Phase 3 trial strong evidence as a	COVID and $\geq 1$ other endpoint:
CoR in vaccine recipients	Highly significant and predictive
-	and Point estimates in the right direction
	for the other endpoints
	Consistent results Day 29, 57 markers
	Require consistent results from multiple trials
5. Phase 3 trial strong supportive evidence	COVID
as CoP, for at least one CoP type,	Point estimates of association/causal parameters
plus point estimates in the right	in the right direction for the other $endpoints^2$
direction for the other CoP types	
(consistency of evidence)	Require consistent results from multiple trials
6. Temporal ordering support for several	
of the above results, e.g., CoRs	
and CoPs are stronger for COVID	COVID , severe COVID ,
occurrence proximal to vaccination	ASYMP-COV-INF, COV-INF, VL Dx
than distal, synchronized with	
pattern of biomarker waning	
7. Additional support from non-vaccine	COVID , severe COVID ,
interventions, e.g., demonstration of	ASYMP-COV-INF, COV-INF, VL Dx
a neutralization CoP for a monoclonal Ab	
 Countervailing evidence could be any obser	vations that provide evidence against a CoP, e.g.,
relative to Bradford-Hill criter	ia (see Section 16).

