In sum, the COV-INF, COVID, and severe COVID endpoints will be analyzed by ordinary survival analysis methods, whereas the asymptomatic infection and non-severe COVID endpoints will be analyzed using competing risks methods. Moreover, adding nomenclature precision, for the parent infection endpoint, the daughter endpoints COVID and asymptomatic infection are semi-competing risks data (nomenclature in the survival analysis literature), and for the COVID parent endpoint, the daughter endpoints severe COVID and non-severe COVID are semi-competing risks data.

In addition, one non-clinical endpoint may be important for correlates assessment: SARS-CoV-2 viral load at COVID diagnosis (VL Dx) (e.g., measured by nasal swab), or alternatively area under the viral load curve (AUC-VL) from the COVID diagnosis date through to undetectable viral load, or to an alternative threshold indicating low viral load. Viral load endpoints are putative surrogates of disease progression and severity for the individual, and are also putative surrogates for secondary transmission; moreover the quantitative nature of viral load endpoints may afford an opportunity to increase statistical power.

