#### Issue 3: Coarseness level of the failure time variable

- 1. **COVID:** Event time defined in 'continuous time' on the day of virological confirmation.
- 2. Asymptomatic infection: Event time defined only at fixed infrequent visits (e.g., Month 6, 12, 18, 24).
- 3. **COV-INF:** Event time defined as 'mixed continuous and discrete', equal to the day of virological confirmation (if COVID) and by the first sero-postive visit (if asymptomatic infection).
- 4. Non-severe COVID: Event time may be defined in continuous time, as the number of days from enrollment to COVID diagnosis plus the number of additional days until the COVID event is known to be non-severe. However, following the decision made for Issue 1, we simplify and define the event time at COVID diagnosis.
- 5. Severe COVID: Event time may be defined in continuous time, as the number of days from enrollment to COVID diagnosis plus the number

of additional days until the COVID event is known to be severe (which may be zero days). However, following the decision made for Issue 1, we simplify and define the event time at COVID diagnosis.

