#### В

Clinical Endpoint	Definition
SARS-CoV-2 infection	Positive RNA PCR test or SARS-CoV-2 seroconversion*, whichever occurs first
COVID (Symptomatic infection)	Meeting a protocol-specified list of COVID-19 symptoms with virological confirmation of SARS-CoV-2 infection (symptom triggered)
Asymptomatic infection	SARS-CoV-2 seroconversion* without prior diagnosis of the COVID endpoint ¶
Severe COVID	COVID endpoint with at least one protocol-specified severe disease event
Non-severe COVID	COVID endpoint with zero protocol-specified severe disease events

\*Seroconversion is assessed via a validated assay that distinguishes natural vs vaccine-induced SARS-CoV-2 antibodies

¶Alternatively, the asymptomatic infection endpoint can also include an RNA PCR+ test result obtained through testing regardless of symptoms (e.g., as a requirement for travel, return to school or work, or elective medical procedures) and follow-up to confirm the participant remains asymptomatic

Figure 1: A) Structural relationships among study endpoints in a COVID-19 vaccine efficacy trial (Mehrotra et al., 2020).. B) Study endpoint definitions.

Figure 2: Example at-COVID diagnosis and post-COVID diagnosis disease severity and virologic sampling schedule, in a setting where frequent follow-up of confirmed cases can be assured. Participants diagnosed with virologically-confirmed symptomatic SARS-CoV-2 infection (COVID) enter a post-diagnosis sampling schedule to monitor viral load and COVID-related symptoms (types, severity levels, and durations).

Figure 3: Case-cohort sampling design (Prentice, 1986) that measures Day 1, 57 antibody markers in all participants selected into the subcohort and in all COVID and COV-INF cases occurring outside of the subcohort.

\* These ≥ 25 cases must have available Day 1, Day 57 antibody marker data and be baseline SARS-CoV-2 negative.
 ¶ bAb and nAb data are measured in all cases, regardless of baseline status.
 ‡ And also potentially of some shorter-term secondary endpoints.

Case-cohort Immunogenicity Analysis Set (ccIAS)

NAAT = nucleic acid amplification test; PCR = polymerase chain reaction; bAb = binding antibody; nAb = neutralizing antibody.

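### COV-INF follow-up continues past the last serotest, when only COVID can be recorded, so COV-INF correlates results are pulled toward the COVID result

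*Combined protocol and SAP*

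**What the plan says.** Section 3.2 states a single right-censoring rule for all correlates of risk (CoR) and correlates of protection (CoP) analyses: "right censoring for a given failure time endpoint will be the first event of loss to follow-up or the date of administrative censoring", with "administrative censoring defined as the last date of available follow-up". CoP follow-up also stops at unblinding. No date tied to serology is given for any endpoint.

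Section 7, Issue 3, describes asymptomatic infection as "Event time defined only at fixed infrequent visits (e.g., Month 6, 12, 18, 24". COV-INF has a mixed event time, "equal to the day of virological confirmation (if COVID) and by the first sero-postive visit (if asymptomatic infection". Issue 2 concludes that "the COV-INF, COVID, and severe COVID endpoints will be analyzed by ordinary survival analysis methods". Figure 1B defines SARS-CoV-2 infection more widely, as "Positive RNA PCR test or SARS-CoV-2 seroconversion*, whichever occurs first".

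On timing, Section 3.2 says there may be enough data for COV-INF and asymptomatic-infection correlates at or shortly after the first correlates analysis. Section 6.1 expects the first reports to be COVID only, and Section 12 defers the special issues of secondary endpoints. Section 25 recognises that seroconversion is interval-censored, but only in notes for Stage 2. Tables 4 and 10 gate each analysis on a minimum of 25, 35 or 50 vaccine-arm endpoints.

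**The concern.** The two components of COV-INF are ascertained over different stretches of follow-up. From a participant's last serotest to the censoring date, a COVID case counts as a COV-INF event, while an asymptomatic infection goes unseen and the time is treated as infection-free. COVID is thus over-represented among COV-INF events.

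If the marker relates more strongly to COVID than to asymptomatic infection, or the vaccine protects better against COVID, the COV-INF estimate moves toward the COVID estimate. Results for a second endpoint would then look more like independent support than they are. This bears on Table 3, where the row beginning "4. Phase 3 trial strong evidence as a" looks for strong evidence on COVID and at least one other endpoint.

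Binary-outcome methods (Sections 12.3.6, 12.4, 14 and 15) are also exposed once extended to these endpoints, because an infection not yet tested for is coded as no event.

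**Working it through.** The plan gives no sample size, event count or effect estimate for COV-INF, so there is no figure to reproduce. The check asks how far the stated rule moves the estimates.

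**Inputs from the plan.** Mock-data defaults (Section 24.3.1): placebo COVID risk 0.10 by 180 days after Day 57 and VE 0.90. Daily hazards are −ln(0.90)/180 = 0.000585 (placebo) and 0.0000585 (vaccine). Serology: Month 6, 12 and so on (Section 7).

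**Assumptions not in the plan.** Month 6 is Day 183, or 126 days after Day 57. The alternative first visit is Day 209 (152 days after), taken from the antibody schedule "over time (Day 1, 29, 57, 209, 394, 759". Follow-up is uniform and there are no incidental PCR positives. The hazard ratio per SD is 0.5 for COVID and 0.9 for asymptomatic infection, with equal baseline hazards in vaccine recipients.

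**1. Cox hazard ratio.** Results for 1.5 million simulated vaccine recipients with a Month 6 first visit:

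| Days followed after Day 57 | COVID HR | COV-INF HR, stated rule | COV-INF HR, censored at last serology | COV-INF events | Events lost |
|---|---|---|---|---|---|
| 90–180 | 0.499 | 0.596 | 0.649 | 21,582 → 14,990 | 31% |
| 180–240 | 0.497 | 0.602 | 0.648 | 33,831 → 24,833 | 27% |
| 180–360 | 0.497 | 0.608 | 0.646 | 44,638 → 34,874 | 22% |

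With every infection ascertained the COV-INF hazard ratio is 0.65. A Day 209 first visit with 90–180 days of follow-up lowers the stated-rule value to about 0.57. For asymptomatic infection the two rules agree: 0.890 and 0.890, 0.900 and 0.900, 0.896 and 0.896.

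**2. Vaccine efficacy.** Assume VE of 94% against COVID and 60% against asymptomatic infection, with 40% of placebo infections asymptomatic. Let c be the share of asymptomatic infections that serology can reveal. For rare events, and ignoring the 7-day lag,

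VE = [0.6 × 0.94 + 0.4 × c × 0.60] / [0.6 + 0.4 × c].

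The true value (c = 1) is 0.804.

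*Binary outcome:* c = (share reaching the visit) × (visit day) / (mean follow-up).
- Month 6, follow-up 90–180: c = 0.60 × 126/135 = 0.56; VE = 0.698/0.824 = 85%.
- Day 209, follow-up 60–180: c = 0.233 × 152/120 = 0.296; VE = 0.635/0.718 = 88%.
- Day 209, follow-up 180–240: c = 152/210 = 0.724; VE = 0.738/0.890 = 83%.

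*Kaplan-Meier at day τ after one serology visit:* c = (visit day)/τ. Participants censored before the visit leave the risk set, so they do not lower c.
- At the visit: c = 1; VE = 80%.
- Day 209, τ = 180: c = 0.844; VE = 0.767/0.938 = 82%.
- Month 6, τ = 240: c = 0.525; VE = 0.690/0.810 = 85%.

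*Range for c = 0.56:* with 30% asymptomatic and 70% VE against it, 89% is read where the truth is 87%. With 50% and 50%, 78% is read where the truth is 72%.

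**3. Before any post-Day 57 serotest.** Here c = 0 and COV-INF equals COVID apart from incidental PCR positives. Under the mock follow-up default of 28 to 45.5 days nobody reaches Month 6, and both Cox fits give 0.507. Tables 4 and 10 count endpoints without asking how many are seroconversions, so COVID cases alone could open a COV-INF analysis.

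**4. Events lost with a later visit.** For Day 209, follow-up 90–180 and equal incidence, 31.1% reach the visit. Events under the stated rule are proportional to 135 + 0.311 × 152 = 182. After truncation they are proportional to 0.311 × 2 × 152 = 95, a loss of about 48%.

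**The case against.** The strongest reply is that the plan knows about this and has postponed it. Section 6.1 expects COVID-only first reports, Section 12 defers secondary endpoints, Section 7 (Issue 4) asks for methods that handle mixed continuous and discrete times, and Section 25 names a partly interval-censored approach. That shows awareness. It does not replace the rule in Section 3.2, which is written for every failure-time endpoint, or the explicit assignment of COV-INF to ordinary survival analysis. The Section 25 method is proposed for longitudinal markers after more than a year of follow-up, not for Day 57 correlates.

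Several stronger readings are tempting, and on these the reply is right:

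- A reader might infer that the censoring rule makes early COV-INF results the COVID result counted twice. That overlap comes from missing serology; censoring at the last serotest would then leave no events at all. Figure 1B also admits non-COVID PCR positives.
- A reader might infer that asymptomatic-infection hazard ratios are biased. Those events occur only at visits, so the risk sets at the visits do not change. Section 12.3.3 also sets t_F near the last observed outcome, which for this endpoint is a serology visit.
- A reader might apply the VE formula with crude person-time coverage to every analysis. That suits binary outcomes; Kaplan-Meier VE at a visit is correct.
- A reader might take Day 209 as the serology schedule, or 28 to 45.5 days as the planned data cut. The first is the antibody-durability schedule and the second a mock-data default.
- A reader might say COV-INF would satisfy Table 3 automatically. The plan calls those requirements conjectural, and that row also needs right-direction estimates for other endpoints and consistency across time points and trials.

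**Conclusion.** The concern holds for COV-INF under Cox regression, for binary-outcome analyses, and for cumulative VE read between serology visits. In the scenarios examined, the hazard ratio per SD is about 0.57 to 0.61 where 0.65 is correct, binary-outcome VE is 83 to 88% where 80% is correct, and Kaplan-Meier VE is 1 to 5 points high after a visit.

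The direction depends on COVID being the component with the stronger marker association or the higher VE. The size depends on assumed effects, asymptomatic share and follow-up, none of which the plan supplies. If the two components behaved alike, the pull would vanish.

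For asymptomatic infection the Cox hazard ratio is not materially affected. Only binary-outcome versions, where unseen infections lower the absolute risk, and missed serotests need attention. Before the first post-Day 57 serotest the difficulty is one of gating: nothing stops a COV-INF analysis that contains almost only COVID events. Since CoP follow-up ends at unblinding, and Section 21 says crossover of placebo recipients has generally been occurring, blinded follow-up could end before that visit.

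**What to change.** Amend Section 3.2 and the place where secondary endpoints are specified:

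1. For COV-INF, and for binary-outcome versions of COV-INF and asymptomatic infection, count events and follow-up only through the last scheduled serology visit reached under blinded follow-up. Censor COVID-free participants at their last completed serotest. Alternatively, adopt a partly interval-censored method such as the one in Section 25.
2. Set t_F for these endpoints at a serology visit.
3. Do not run COV-INF correlates, or cite them as corroboration separate from COVID, until a post-Day 57 serology visit has been reached under blinded follow-up. Add this condition to Tables 4 and 10.

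The cost is SAP wording and a second censoring variable. Truncation removes COVID events after the last serotest from the COV-INF analysis: roughly 26 to 50% of COV-INF events in most of the simulated scenarios, and 22% with follow-up of 180 to 360 days. They all remain in the COVID analysis. A partly interval-censored method would keep them in COV-INF, at the price of a more complex model under two-phase sampling.

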#### 3.2.1 [With Day 29 markers]

If Day 29 markers are included, analyses that study Day 29 markers count study endpoints starting 7 days post Day 29 visit, instead of starting 7 days post Day 57 visit. Analyses that include both Day 29 and Day 57 markers (for correlates analyses this only includes the multivariable correlates of risk superlearning objective) use the same cohort and endpoints as analyses of Day 57 markers only.

# 4 Objectives of Immune Correlates Analyses of a Phase 3 Trial Data Set

#### 4.1 Characterize Vaccine Immunogenicity

There are two objectives to characterize the binding and neutralizing antibody immunogenicity of the vaccine:

Stage 1 To characterize vaccine immunogenicity (bAb, nAb) at Day 1, 29, 57

Stage 2 To characterize vaccine immunogenicity/durability (bAb, nAb) over time (Day 1, 29, 57, 209, 394, 759)

